### 11.1.2. Patient Background

Item	Category	Note
Sex	Male, Female	
Age 1	<65 years, $\geq$ 65 years	Continuous data
Age 2	<50 years, $\geq$ 50 years to <65 years, $\geq$ 65 years	
Age 3	<40 years, $\geq$ 40 years to <50 years, $\geq$ 50 years to <60 years, $\geq$ 60 years to <70 years, $\geq$ 70 years to <80 years, $\geq$ 80 years	

Item	Category	Note
Age 4	<50 years, $\geq$ 50 years to <60 years, $\geq$ 60 years to <70 years, $\geq$ 70 years	
Height	<140 cm, $\geq$ 140 cm to <150 cm, $\geq$ 150 cm to <160 cm, $\geq$ 160 cm to <170 cm, $\geq$ 170 cm to <180 cm, $\geq$ 180 cm, Not measured	Continuous data
Body weight 1	<40 kg, $\geq$ 40 kg to <50 kg, $\geq$ 50 kg to <60 kg, $\geq$ 60 kg to <70 kg, $\geq$ 70 kg to <80 kg, $\geq$ 80 kg, Not measured	Continuous data
Body weight 2	<50 kg, $\geq$ 50 kg to <60 kg, $\geq$ 60 kg to <70 kg, $\geq$ 70 kg, Not measured	
BMI	<18.5, $\geq$ 18.5 to <25, $\geq$ 25	Continuous data
Inpatient/outpatient	Inpatient, Outpatient	
Disease to be investigated	Rheumatoid arthritis, Others	
Stage of rheumatoid arthritis	I, II, III, IV	
	I,-II, III, IV	
Class of rheumatoid arthritis	1, 2, 3, 4	
	1- 2, 3, 4	
Duration of disease 1	<6 months, $\geq$ 6 months to <2 years, $\geq$ 2 years to <5 years, $\geq$ 5 years to <10 years, $\geq$ 10 years to <20 years, $\geq$ 20 years, Unknown	Continuous data
Duration of disease 2	<2 years, $\geq$ 2 years to <5 years, $\geq$ 5 years to <10 years, $\geq$ 10 years to <20 years, $\geq$ 20 years, Unknown	
Past history	Absent, Present	
Past history (infection)	Absent, Present	
Past history (herpes zoster)	Absent, Present	
Past history (tuberculosis-related disease)	Absent, Present	
Past history (malignant tumor)	Absent, Present	
Past history (autoimmune disease)	Absent, Present	
Past history (Sjogren's syndrome)	Absent, Present	

Item	Category	Note
Past history (cardiovascular disease)	Absent, Present	
Past history (hypertension)	Absent, Present	
Past history (angina pectoris)	Absent, Present	
Past history (myocardial infarction)	Absent, Present	
Past history (heart failure)	Absent, Present	
Past history (arrhythmia)	Absent, Present	
Past history (pulmonary disorder)	Absent, Present	
Past history (interstitial pneumonia)	Absent, Present	
Past history (gastrointestinal disorder)	Absent, Present	
Past history (diverticulum)	Absent, Present	
Past history (gastrointestinal perforation)	Absent, Present	
Past history (hepatic dysfunction)	Absent, Present	
Past history (hepatitis B)	Absent, Present	
Past history (hepatitis C)	Absent, Present	
Past history (other hepatitis)	Absent, Present	
Past history (hepatitis B virus carrier)	Absent, Present	
Past history (hepatitis C virus carrier)	Absent, Present	
Past history (other hepatitis virus carrier)	Absent, Present	
Past history (renal dysfunction)	Absent, Present	
Past history (metabolic abnormality)	Absent, Present	
Past history (diabetes mellitus)	Absent, Present	

Item	Category	Note
Past history (lipid abnormality)	Absent, Present	
Past history (anemia)	Absent, Present	
Past history (others)	Absent, Present	
Complication	Absent, Present	
Complication (infection)	Absent, Present	
Complication (herpes zoster)	Absent, Present	
Complication (tuberculosis-related disease)	Absent, Present	
Complication (malignant tumor)	Absent, Present	
Complication (autoimmune disease)	Absent, Present	
Complication (Sjogren's syndrome)	Absent, Present	
Complication (cardiovascular disease)	Absent, Present	
Complication (hypertension)	Absent, Present	
Complication (angina pectoris)	Absent, Present	
Complication (myocardial infarction)	Absent, Present	
Complication (heart failure)	Absent, Present	
Complication (arrhythmia)	Absent, Present	
Complication (pulmonary disorder)	Absent, Present	
Complication (interstitial pneumonia)	Absent, Present	
Complication (gastrointestinal disorder)	Absent, Present	
Complication (diverticulum)	Absent, Present	
Complication (gastrointestinal perforation)	Absent, Present	

Item	Category	Note
Complication (hepatic dysfunction)	Absent, Present	
Complication (hepatitis B)	Absent, Present	
Complication (hepatitis C)	Absent, Present	
Complication (other hepatitis)	Absent, Present	
Complication (hepatitis B virus carrier)	Absent, Present	
Complication (hepatitis C virus carrier)	Absent, Present	
Complication (other hepatitis virus carrier)	Absent, Present	
Complication (renal dysfunction)	Absent, Present	
Complication (metabolic abnormality)	Absent, Present	
Complication (diabetes mellitus)	Absent, Present	
Complication (lipid abnormality)	Absent, Present	
Complication (anemia)	Absent, Present	
Complication (others)	Absent, Present	
Smoking history 1	Absent, Present, Unknown	
Smoking history 2	Past history absent, Past history present, Present, Unknown	
Family history of malignant tumors (including lymphoma)	Absent, Present, Unknown	
History of MTX use (Within 3 months prior to the start of survey)	Absent, Present, (History) Unknown	
History of MTX use (Dose just prior to the start of survey 1)	Absent, >0 mg to $\leq$ 8 mg/week, >8 mg/week	Continuous data

Item	Category	Note
History of MTX use (Dose just prior to the start of survey 2)	Absent, >0 mg to $\leq$ 2 mg/week, >2 mg to $\leq$ 4 mg/week, >4 mg to $\leq$ 6 mg/week, >6 mg to $\leq$ 8 mg/week, >8 mg to $\leq$ 10 mg/week, >10 mg to $\leq$ 12 mg/week, >12 mg to $\leq$ 14 mg/week, >14 mg to $\leq$ 16 mg/week, >16mg/week	
History of MTX use (Duration)	Absent, <6 months, $\geq$ 6 months to <3 years, $\geq$ 3 years to <5 years, $\geq$ 5 years, (Duration) Unknown, (History) Unknown	
Status of MTX use (Dose prior to the start date of survey 1)	Absent, >0 mg to $\leq$ 8 mg/week, >8 mg/week	Continuous data A weekly dose specified for the period including the day on which administration of Xeljanz starts Summary statistics should be calculated also under an assumption that patients with absence of data are excluded.
Status of MTX use (Dose prior to the start date of survey 2)	Absent, >0 mg to $\leq$ 2 mg/week, >2 mg to $\leq$ 4 mg/week, >4 mg to $\leq$ 6 mg/week, >6 mg to $\leq$ 8 mg/week, >8 mg to $\leq$ 10 mg/week, >10 mg to $\leq$ 12 mg/week, >12 mg to $\leq$ 14 mg/week, >14 mg to $\leq$ 16 mg/week, >16mg/week	
History of oral steroid use (Within 3 months prior to the start of survey)	Absent, Present	The presence/absence of oral steroid use within 90 days prior to the start of administration of Xeljanz (including the date of the initiation of administration) will be calculated.
History of oral steroid use (Dose just prior to the start of survey 1)	Absent , >0 mg/day to <2.5 mg/day, $\geq$ 2.5 mg/day to <5 mg/day, $\geq$ 5 mg/day	Daily dose that is prior to the start of survey, is within the dosing period of steroid, and includes the day closest to the

Item	Category	Note
History of oral steroid use (Dose just prior to the start of survey 2)	Absent , >0 mg/day to <5 mg/day, $\geq 5$ mg/day	survey start. Summarize based on prednisolone equivalent dose (= $5 \times$ Dose/Pharmacologically equivalent strength) Pharmacologically equivalent strengths: hydrocortisone=20, cortisone=25, prednisone=5, prednisolone=5, methylprednisolone=4, triamcinolone=4, paramethasone=2, dexamethasone=0.75, betamethasone =0.6 
History of oral steroid use (Duration)	Absent, <6 months, $\geq 6$ months to <3 years, $\geq 3$ years, (Duration) Unknown, (History) Unknown	
Status of oral steroid use (Dose prior to the start date of survey 1)	Absent , >0 mg/day to <2.5 mg/day, $\geq 2.5$ mg/day to <5 mg/day, $\geq 5$ mg/day	Daily dose that is prior to the start of survey, is within the dosing period of steroid, and includes the day closest to the survey start.
Status of oral steroid use (Dose prior to the start date of survey 2)	Absent , >0 mg/day to <5 mg/day, $\geq 5$ mg/day	Summarize based on prednisolone equivalent dose (= $5 \times$ Dose/Pharmacologically equivalent strength) Pharmacologically equivalent strengths: hydrocortisone=20, cortisone=25, prednisone=5, prednisolone=5, methylprednisolone=4, triamcinolone=4, paramethasone=2, dexamethasone=0.75, betamethasone =0.6 
History of tacrolimus use	Absent, Present	
History of tacrolimus use (Duration)	Absent, <6 months, $\geq 6$ months to <3 years, $\geq 3$ years, (Duration) Unknown, (History) Unknown	

Item	Category	Note
Past use of biological agents (Within 3 months prior to the start of survey)	Absent, Present	
Initial daily dose of Xeljanz [mg]	5 mg, 10 mg, >10 mg	Xeljanz group only
White blood cell count [/mm  ] [/mm  ]	<4000, ≥ 4000	Data that is prior to the start of survey, and the day closest to the survey start.
Neutrophil count [/mm  ]	<500, ≥500 to <1000, ≥1000	Data that is prior to the start of survey, and the day closest to the survey start.
	<4000, ≥ 4000	
Lymphocyte count [/mm  ]	<500, ≥500 to <1000, ≥1000	Data that is prior to the start of survey, and the day closest to the survey start.
	<1500, ≥1500	
Hemoglobin [g/dL]	<8, ≥8 to <9, ≥10	Data that is prior to the start of survey, and the day closest to the survey start.
β-D-glucan	Positive, Negative	Data that is prior to the start of survey, and the day closest to the survey start.
Chest X-ray or chest CT	Performed, Not performed	Xeljanz group only
Tuberculosis test	Performed, Not performed	Xeljanz group only  Any of the above chest X-ray or chest CT, interferon γ, and tuberculin reaction will be performed.
Interferon γ	QuantiFERON, T-spot, TB Positive, assessment pending, or Negative for each	Xeljanz group only
Tuberculin reaction	-, 1+, 2+, 3+	Xeljanz group only
Systolic blood pressure	<120 mmHg, ≥120 mmHg to <140 mmHg, ≥140 mmHg to <160 mmHg, ≥160 mmHg to <180 mmHg, ≥180 mmHg	Continuous data  Xeljanz group only
Diastolic blood pressure	<60 mmHg, ≥60 mmHg to <80 mmHg, ≥80 mmHg to <100 mmHg, ≥100 mmHg to <120 mmHg, ≥120 mmHg to <140 mmHg, ≥140 mmHg	Continuous data  Xeljanz group only
HBs antigen	No data, Positive, Negative	Xeljanz group only
HBs antibody	No data, Positive, Negative	Xeljanz group only
HBc antibody	No data, Positive, Negative	Xeljanz group only
HBV-DNA test [log copy/mL]	No data, <2.6, ≥2.6	Xeljanz group only
HCV antibody	No data, Positive, Negative	Xeljanz group only

Item	Category	Note
Hepatitis B and C virus test	Performed, Not performed	Xeljanz group only Any of the above HBs antigen, HBs antibody, HBc antibody, HBV-DNA test, and HCV antibody will be performed.
Prophylactic administration to prevent tuberculosis	Performed, Not performed	
Prophylactic administration to prevent pneumocystis jiroveci pneumonia	Performed, Not performed	
Prophylactic administration to prevent hepatitis B	Performed, Not performed	
SDAI	$\leq 3.3$ , $>3.3$ to $\leq 11$ , $>11$ to $\leq 26$ , $>26$ $\leq 11$ , $>11$ to $\leq 26$ , $>26$	Continuous data Xeljanz group only
CDAI	$\leq 2.8$ , $>2.8$ to $\leq 10$ , $>10$ to $\leq 22$ , $>22$ $\leq 10$ , $>10$ to $\leq 22$ , $>22$	Continuous data Xeljanz group only
DAS28	$<2.6$ , $\geq 2.6$ to $<3.2$ , $\geq 3.2$ to $\leq 5.1$ , $>5.1$ $<3.2$ , $\geq 3.2$ to $\leq 5.1$ , $>5.1$	Continuous data Xeljanz group only
Organization that established the hospital	University hospitals, National hospitals established by the Ministry of Health, Labour and Welfare, Prefectural and municipal hospitals, Public institutions, Hospitals other than the above 4 hospitals established by companies and individuals, General practitioners and clinics	

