Name of drug (product name), dosage (MTX, Oral steroids), duration of treatment, and reason for treatment (Other drugs)

\*Please do not coadminister biological preparations and immunosuppressants along with Xeljanz.

[Surgical treatment of rheumatoid arthritis]

Name of the surgical therapy for rheumatoid arthritis, the date of operation, and the reason for operation should be recorded.

- (5) Whether or not pneumococcus vaccine has been administered (both groups). \*Until 12 months after surveillance start in control group
- (6) Prophylactic administration to prevent tuberculosis, pneumocystis jiroveci pneumonia, and hepatitis B (nucleic acid analogs) (both groups). \*For control group, until 12 months after surveillance start

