### **5.4. Subgroups**

For the Xeljanz group, safety and efficacy will be analyzed for each of the following subgroups.

- Sex
- Age class ( $\geq 65$  years,  $< 65$  years)
- Presence or absence of hepatic dysfunction (Presence of hepatic dysfunction is defined as the item “current hepatic dysfunction” in the medical history being checked.)
- Presence or absence of renal dysfunction (Presence of renal dysfunction is defined as the item “current renal dysfunction” in the medical history being checked.)
- Average actual daily dose ( $< 7.5$  mg,  $\geq 7.5$  mg)

Patients that may be contraindicated in the package insert of Xeljanz (hereinafter referred to as contraindicated patients) are extracted based on the criteria specified separately, and a subpopulation analysis of safety is performed.

In addition, safety and efficacy will be analyzed for each of the patient background subgroups specified in Appendix 11.1.3 and 11.1.4.

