### Ordinal Scale

Item	Category	Note
Age 3	<40 years, $\geq$ 40 years to <50 years, $\geq$ 50 years to <60 years, $\geq$ 60 years to <70 years, $\geq$ 70 years to <80 years, $\geq$ 80 years	Reference: <40 years
Age 4	<50 years, $\geq$ 50 years to <60 years, $\geq$ 60 years to <70 years, $\geq$ 70 years	Reference: <50 years
Body weight 2	<50 kg, $\geq$ 50 kg to <60 kg, $\geq$ 60 kg to <70 kg, $\geq$ 70 kg	Reference: <50 kg
BMI	<18.5, $\geq$ 18.5 to <25, $\geq$ 25	Reference: <18.5
Stage of rheumatoid arthritis	I, II, III, IV	Reference: I
	I- II, III, IV	Reference: I- II
Class of rheumatoid arthritis	1, 2, 3, 4	Reference: 1
	1-2, 3, 4	Reference: 1-2
Duration of disease 2	<2 years, $\geq$ 2 years to <5 years, $\geq$ 5 years to <10 years, $\geq$ 10 years to <20 years, $\geq$ 20 years	Reference: <2 years
History of MTX use (Dose just prior to the start of survey 1)	Absent, >0 mg to $\leq$ 8 mg/week, >8 mg/week	Reference: Absent
History of MTX use (Dose just prior to the start of survey 2)	Absent, >0 mg to $\leq$ 2 mg/week, >2 mg to $\leq$ 4 mg/week, >4 mg to $\leq$ 6 mg/week, >6 mg to $\leq$ 8 mg/week, >8 mg to $\leq$ 10 mg/week, >10 mg to $\leq$ 12 mg/week, >12 mg to $\leq$ 14 mg/week, >14 mg to $\leq$ 16 mg/week, >16 mg/week	Reference: Absent
History of MTX use (Duration)	Absent, <6 months, $\geq$ 6 months to <3 years, $\geq$ 3 years to <5 years, $\geq$ 5 years	Reference: Absent
Status of MTX use (Dose prior to the start date of survey 1)	Absent, >0 mg to $\leq$ 8 mg/week, >8 mg/week	Reference: Absent
Status of MTX use (Dose prior to the start date of survey 2)	Absent, >0 mg to $\leq$ 2 mg/week, >2 mg to $\leq$ 4 mg/week, >4 mg to $\leq$ 6 mg/week, >6 mg to $\leq$ 8 mg/week, >8 mg to $\leq$ 10 mg/week, >10 mg to $\leq$ 12 mg/week, >12 mg to $\leq$ 14 mg/week, >14 mg to $\leq$ 16 mg/week, >16 mg/week	Reference: Absent
History of oral steroid use (Dose just prior to the start of survey 1)	Absent, >0 mg/day to <2.5 mg/day, $\geq$ 2.5 mg/day to <5 mg/day, $\geq$ 5 mg/day	Reference: Absent
History of oral steroid use (Dose just prior to the start of survey 2)	Absent, >0 mg/day to <5 mg/day, $\geq$ 5 mg/day	Reference: Absent
Status of oral steroid use (Dose prior to the start date of survey 1)	Absent, >0 mg/day to <2.5 mg/day, $\geq$ 2.5 mg/day to <5 mg/day, $\geq$ 5 mg/day	Reference: Absent
Status of oral steroid use (Dose prior to the start date of survey 2)	Absent, >0 mg/day to <5 mg/day, $\geq$ 5 mg/day	Reference: Absent

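### In SAP 11.1.2 the oral steroid Status rows repeat the History definition, so one safety factor is tested twice and no visible item gives steroid dose on the start day

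*SAP*

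**What the plan says.** SAP 11.1.2 describes prior and current use of MTX and of oral steroids through paired History and Status rows, each in a version 1 and a version 2 that differ only in how the dose is grouped.

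- **MTX Status.** The note reads "A weekly dose specified for the period including the day on which administration of Xeljanz starts".
- **Steroid History.** The note reads "Daily dose that is prior to the start of survey, is within the dosing period of steroid, and includes the day closest"; the rest of the sentence, split by a page break, names the survey start. A prednisolone-equivalent conversion follows.
- **Steroid Status.** The note reads "Daily dose that is prior to the start of survey, is within the dosing period of steroid, and includes the day closest to the survey"; its last word and the conversion after it are the same as for History.

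SAP 11.1.3 lists both steroid pairs among the ordinal safety factors, for example "History of oral steroid use (Dose just prior to the start of survey 1" and, as a separate row, "Status of oral steroid use (Dose prior to the start date of survey 1", with the same categories and Absent as the reference for both. SAP 5.4 states that "safety and efficacy will be analyzed for each of the patient background subgroups specified in Appendix 11.1.3 and 11.1.4". SAP 8.2.3.2 tabulates and tests every 5.4 factor for each of 11 adverse drug reaction groups, and 8.1.3 assigns the exact Cochran-Armitage test to ordinal factors.

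For the Xeljanz group, Protocol 7.1 (Survey form, Concomitant therapy) collects "Name of drug (product name), dosage (MTX, Oral steroids), duration of treatment" from 3 months before the start of treatment.

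**The concern.** Two rows with different names ought to measure different things, and the MTX rows show the distinction the SAP draws: History looks back from the start, while Status describes the treatment period running on the day Xeljanz begins. The steroid rows keep the two names but give them one definition. A reader of the 11.1.3 tables would see two apparently separate steroid-dose results that agree perfectly, and could take that as corroboration when it is one variable printed twice.

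The start-day dose is also left without a variable of its own. Protocol Section 1 makes factors that may affect safety part of the first objective, and the 8.2.3.2 event list includes serious infections and herpes zoster, for which steroid dose at the start of Xeljanz is an obvious candidate factor.

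**Working it through.** The documents give no figure to reproduce. The check is a comparison of definitions, a trace into the analysis and a count.

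**1. Are the definitions the same?** With the History note rejoined across the page break, its defining sentence matches the Status sentence exactly. The conversion text matches too. The categories are the same in both pairs: version 1 is Absent, >0 to <2.5, ≥2.5 to <5 and ≥5 mg/day; version 2 is Absent, >0 to <5 and ≥5 mg/day.

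**2. Does the label explain the difference from MTX?** No. The MTX and steroid Status rows carry the same parenthetical label, which refers to the dose before the survey start date. Under that label MTX takes the period containing the start day and steroids take a pre-start dose.

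**3. Who is classified differently?** The present steroid note compared with an MTX-type rule:

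| Steroid course | Present Status note | Period including Day 1 |
|---|---|---|
| Stable dose through the start | Current dose | Current dose |
| Started or changed before the start, then continued | New dose | New dose |
| Ended before Day 1 | Last dose taken | Absent |
| Started on Day 1, none recorded earlier | Absent | Day 1 dose |
| Changed on Day 1 | Old dose | New dose |

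Only the last three rows differ.

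**4. How many tests repeat?** SAP 11.1.3 has 4 steroid-dose rows (History 1 and 2, Status 1 and 2). SAP 8.2.3.2 lists 11 event groups.

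- Tests listed, going once through the event list: 4 × 11 = 44.
- Distinct tests: 2 × 11 = 22.
- Exact repeats: 44 − 22 = 22.

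Versions 1 and 2 are two groupings of one dose and are not counted as duplicates.

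**5. Is start-day dose available elsewhere?** The only visible steroid item whose definition includes the start day is use within 90 days, which is presence or absence without dose (11.1.2). Concomitant oral steroids are tabulated as number and proportion of patients (8.2.2).

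**6. Does it reach the group comparison?** SAP 6.3 enters steroids only as use within 3 months before the start. The adjusted hazard ratio (8.2.3.1.1, 8.2.3.1.2) and the propensity score (8.1.6) draw on 6.3, not on the dose rows. SAP 11.1.4 has no steroid-dose row, so the efficacy factor analyses are untouched.

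**The case against.** The best defence is that little is lost. A patient on a continuing, unchanged steroid gets the right dose under the present note, and so does one who changed before the start and stayed on the new dose. Data collection limits the look-back to about 3 months. SAP Section 4 declares all tests exploratory, and exact repeats return identical results, so they do not inflate the type I error. The steroid Status label itself speaks of a dose before the start date, so a pre-start dose fits its wording, and deleting the rows would remove the inconsistency equally well. In the control group oral steroids are part of the treatment record (Protocol 7.1, Dose record), so a Day 1 dose there could mix baseline use with the new regimen.

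All of this stands as a limit on the impact, and the last point restricts where a start-day definition should apply. None of it explains why the SAP reports one variable under two names.

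A reader might go further and infer that steroid dose at the start is never analysed, or that every patient with a steroid change around the start is misclassified. The documents support neither. For stable patients the recorded dose is the start-day dose, changes made before the start and continued are captured, and parts of the SAP analysis text are redacted.

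**Conclusion.** The point holds as a duplicated definition with a limited effect. As written, half of the listed steroid-dose tests (22 of 44) repeat the other half, and no unredacted item gives the steroid dose on the start day. The Status rows are wrong for patients whose steroid ended before Day 1, or was started or changed on Day 1, if Status is meant as it is for MTX. That intention is inferred from the parallel MTX rows; a copied note is the likeliest explanation.

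The documents do not state the share of patients affected. A reader might want to express the misclassification as a given dilution of a steroid risk ratio, but any such figure would rest on an assumed share and on assumed risks, so none is offered. Nor should the point be read as a threat to the comparison with the control group. It concerns only the exploratory factor analyses in the Xeljanz group.

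**What to change.** For the Xeljanz-group factor analyses in SAP 11.1.3, give the steroid Status rows their own note in 11.1.2: the prednisolone-equivalent daily dose for the dosing period that includes Day 1, with Absent if there is none, in parallel to the MTX Status rows. Keep the present note for the History rows only. If a start-day dose is not wanted, delete the duplicate Status rows from 11.1.2 and 11.1.3, which leaves 22 distinct tests.

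The cost is one note and a re-run of the steroid rows in the factor tables. Steroid dosage and treatment duration from 3 months before the start are already collected in the Xeljanz group.

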### 11.1.3. Patient Background Considered for Safety

#### Nominal Scale

Item	Category	Note
Sex	Male, Female	Reference: Male
Age 1	$<65$ years, $\geq 65$ years	Reference: $<65$ years
Past history (infection)	Absent, Present	Reference: Absent
Past history (herpes zoster)	Absent, Present	Reference: Absent

## Nominal Scale

Item	Category	Note
Past history (tuberculosis-related disease)	Absent, Present	Reference: Absent
Past history (malignant tumor)	Absent, Present	Reference: Absent
Past history (autoimmune disease)	Absent, Present	Reference: Absent
Past history (Sjogren's syndrome)	Absent, Present	Reference: Absent
Past history (cardiovascular disease)	Absent, Present	Reference: Absent
Past history (hypertension)	Absent, Present	Reference: Absent
Past history (angina pectoris)	Absent, Present	Reference: Absent
Past history (myocardial infarction)	Absent, Present	Reference: Absent
Past history (heart failure)	Absent, Present	Reference: Absent
Past history (arrhythmia)	Absent, Present	Reference: Absent
Past history (pulmonary disorder)	Absent, Present	Reference: Absent
Past history (interstitial pneumonia)	Absent, Present	Reference: Absent
Past history (gastrointestinal disorder)	Absent, Present	Reference: Absent
Past history (diverticulum)	Absent, Present	Reference: Absent
Past history (gastrointestinal perforation)	Absent, Present	Reference: Absent
Past history (hepatic dysfunction)	Absent, Present	Reference: Absent
Past history (hepatitis B)	Absent, Present	Reference: Absent
Past history (hepatitis C)	Absent, Present	Reference: Absent
Past history (other hepatitis)	Absent, Present	Reference: Absent
Past history (hepatitis B virus carrier)	Absent, Present	Reference: Absent
Past history (hepatitis C virus carrier)	Absent, Present	Reference: Absent
Past history (other hepatitis virus carrier)	Absent, Present	Reference: Absent
Past history (renal dysfunction)	Absent, Present	Reference: Absent
Past history (metabolic abnormality)	Absent, Present	Reference: Absent
Past history (diabetes mellitus)	Absent, Present	Reference: Absent
Past history (lipid abnormality)	Absent, Present	Reference: Absent
Past history (anemia)	Absent, Present	Reference: Absent
Complication (infection)	Absent, Present	Reference: Absent
Past history (herpes zoster)	Absent, Present	Reference: Absent

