**Table 3. Categories of Tabulation Items for the Status of the Implementation of Tests**

Item	Category
Test	Test (implemented if at least one is met), chest X-ray or chest CT (chest X-ray, chest CT), interferon $\gamma$ or tuberculin reaction (interferon $\gamma$ , tuberculin reaction), hepatitis B and C virus test (HBs antigen, HBs antibody, HBc antibody, HBV-DNA test, HCV antibody)
Test timing	after the initiation of administration of Xeljanz (Day 2-), before the initiation of administration of Xeljanz $\leq$ 3 months (Day -30 to Day 0), before the initiation of administration of Xeljanz $>$ 3 months (-Day 31), before the initiation of administration of Xeljanz $>$ 3 months to $\leq$ 6 months (Day -183 to Day -31), before the initiation of administration of Xeljanz $>$ 6 months to $\leq$ 12 months (Day -364 to Day -182), before the initiation of administration of Xeljanz $>$ 12 months to $\leq$ 24 months (Day -729 to Day -365), before the initiation of administration of Xeljanz $>$ 24 months (-Day -730)

- Past medical histories**

In the safety analysis set, the number and proportion of patients with past medical histories will be calculated for each system organ class (SOC) and preferred term (PT).

- Complications**

In the safety analysis set, the number and proportion of patients with complications (current medical history) will be calculated for each SOC and PT.

- Concomitant drugs**

In the safety and efficacy analysis sets in the Xeljanz group, the number and proportion of patients who used concomitant drugs will be calculated. A biological therapeutic or immunosuppressant terminated on the same day as the first dose of Xeljanz or started on the same day as the last dose of Xeljanz will not be considered as a concomitant drug.

Similarly, the number and the proportion of patients will be calculated by methotrexate (MTX), biological agents, DMARDs and immunosuppressive agents other than MTX, oral steroids and other drugs.

- Non-drug therapies**

In the safety and efficacy analysis sets in the Xeljanz group, the number and proportion of patients who underwent surgical therapies for rheumatoid arthritis (surgery scheduled before the initiation of this survey) will be calculated.

- **Prior medications**

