**Table 8. Tabulation Items Concerning the Details of Adverse Drug Reactions by Event**

Item	Category	Order of precedence
Seriousness	Serious, non-serious	Serious → non-serious
Known/unknown	Known, unknown	Unknown → known
Outcome	Resolved/recovered, recovering, recovered with sequel, not recovered, unknown	An event that last developed
Number of days to onset	Start of treatment - 1 month (Day 1 to Day 31), 1 month< - 3 months (Day 32 to Day 92), 3 months< - 6 months (Day 93 to Day 184), 6 months< - 9 months (Day 185 to Day 275), 9 months< - 12 months (Day 276 to Day 366), 12 months< - 18 months (Day 367 to Day 549), 18 months< - 24 months (Day 550 to Day 731), 24 months< - 30 months (Day 732 to Day 914), 30 months< - 36 months (Day 914 to Day 1096), >36 months (Day 1097-)	An event that first developed
Change in administration of Xeljanz	No change, dose reduction, temporary suspension, discontinuation	Discontinuation → temporary suspension → dose reduction → no change

• **Subgroup analysis**

The number and proportion of patients with at least 1 following each adverse drug reaction will be tabulated for each factor specified in [Section 5.4](#) in accordance with [Section 8.1.3](#). Tests will be performed between the levels of each background factor.

- Serious infections;
- Neutrophil count decreased and neutropenia;
- Lymphocyte count decreased and lymphopenia;
- Hemoglobin decreased and anemia;
- Lipid increased and hyperlipidemia;
- Malignant tumors (including lymphoma);
- Gastrointestinal perforation;
- Cardiovascular adverse events;
- Hepatic dysfunction;
- Interstitial pneumonia;
- Herpes Zoster.

The following tabulation and analysis will be performed for sex, age class and each subgroup in patients with and without hepatic dysfunction and patients with and without renal dysfunction:

- Development of adverse drug reactions;
- Development of serious adverse drug reactions;
- Development of serious adverse events.

A list of adverse reactions for contraindicated patients are created. Furthermore, if necessary, the number of patient with adverse reactions and their proportions are calculated for each SOC and PT.

- **Key survey items**

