## Nominal Scale

Item	Category	Note
Past history (tuberculosis-related disease)	Absent, Present	Reference: Absent
Complication (malignant tumor)	Absent, Present	Reference: Absent
Complication (autoimmune disease)	Absent, Present	Reference: Absent
Complication (Sjogren's syndrome)	Absent, Present	Reference: Absent
Complication (cardiovascular disease)	Absent, Present	Reference: Absent
Complication (hypertension)	Absent, Present	Reference: Absent
Complication (angina pectoris)	Absent, Present	Reference: Absent
Complication (myocardial infarction)	Absent, Present	Reference: Absent
Complication (heart failure)	Absent, Present	Reference: Absent
Complication (arrhythmia)	Absent, Present	Reference: Absent
Complication (pulmonary disorder)	Absent, Present	Reference: Absent
Complication (interstitial pneumonia)	Absent, Present	Reference: Absent
Complication (gastrointestinal disorder)	Absent, Present	Reference: Absent
Complication (diverticulum)	Absent, Present	Reference: Absent
Complication (gastrointestinal perforation)	Absent, Present	Reference: Absent
Complication (hepatic dysfunction)	Absent, Present	Reference: Absent
Complication (hepatitis B)	Absent, Present	Reference: Absent
Complication (hepatitis C)	Absent, Present	Reference: Absent
Complication (other hepatitis)	Absent, Present	Reference: Absent
Complication (hepatitis B virus carrier)	Absent, Present	Reference: Absent
Complication (hepatitis C virus carrier)	Absent, Present	Reference: Absent
Complication (other hepatitis virus carrier)	Absent, Present	Reference: Absent
Complication (renal dysfunction)	Absent, Present	Reference: Absent
Complication (metabolic abnormality)	Absent, Present	Reference: Absent
Complication (diabetes mellitus)	Absent, Present	Reference: Absent
Complication (lipid abnormality)	Absent, Present	Reference: Absent
Complication (anemia)	Absent, Present	Reference: Absent
Smoking history 1	Absent, Present	Reference: Absent

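### SAP Appendix 11.1.3 repeats the past-history rows for herpes zoster and tuberculosis where the current-illness rows belong, so neither current condition is listed as a separate safety subgroup factor

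*SAP*

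**What the plan says.** SAP Section 5.4 makes Appendix 11.1.3 an operative list: "safety and efficacy will be analyzed for each of the patient background subgroups specified in Appendix 11.1.3 and 11.1.4". SAP Section 8.2.3.2 (Subgroup analysis) then tabulates 11 types of adverse drug reaction by each Section 5.4 factor and adds: "Tests will be performed between the levels of each background factor".

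In the SAP a complication is a current illness. Section 8.2.2 (Complications, after Table 3) states that "the number and proportion of patients with complications (current medical history) will be calculated for each SOC and PT".

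Appendix 11.1.2, the descriptive background list, has a past-history block and a complication block that carry the same diseases in the same order. Its complication block includes "Complication (herpes zoster" and "Complication (tuberculosis-related disease". Appendix 11.1.3 follows the same order, but directly after "Complication (infection" it prints "Past history (herpes zoster" and "Past history (tuberculosis-related disease" for a second time.

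In the hemoglobin row of 11.1.2 the three classes are below 8, 8 to below 9, and 10 or above (g/dL).

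**The concern.** Factors that may affect safety are part of the first objective (Protocol Section 1). The first key survey item is serious infection, expressly including herpes zoster and tuberculosis (Protocol Section 7.8), and herpes zoster is also one of the 11 tested reaction types in SAP Section 8.2.3.2. A programmer who follows 11.1.3 literally would request the same two past-history analyses twice and would produce no separate analysis of patients who have herpes zoster or tuberculosis at the start. The other 27 current illnesses on the list would each have one. These two conditions lie close to the leading safety question, so the list should be right even though the tests are exploratory.

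The hemoglobin gap is a smaller, separate slip: a patient with a baseline value from 9 to below 10 g/dL fits no class in that row.

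**Working it through.** No sample size, power or error rate is involved. The check is a row-by-row comparison of the two lists.

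**Inputs.** The disease-specific past-history and complication rows of SAP 11.1.2 and of SAP 11.1.3 (Nominal Scale). The overall present/absent rows and the rows for other diseases appear only in 11.1.2 and are left out of the count.

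**Start of the complication block, side by side.**

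| Position | 11.1.2 | 11.1.3 |
|---|---|---|
| 1 | complication: infection | complication: infection |
| 2 | complication: herpes zoster | past history: herpes zoster |
| 3 | complication: tuberculosis-related | past history: tuberculosis-related |
| 4 | complication: malignant tumor | complication: malignant tumor |

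From position 4 on, the two blocks agree to the end (anemia).

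**Counts.**
- 11.1.2: 29 past-history + 29 complication = 58 rows, all distinct.
- 11.1.3: 29 + 2 = 31 past-history rows and 29 − 2 = 27 complication rows. 31 + 27 = 58 rows, of which 58 − 2 = 56 are distinct.
- Items in 11.1.2 but not in 11.1.3: exactly two, current herpes zoster and current tuberculosis-related disease.
- After relabelling the two duplicates: 29 + 29 = 58 distinct items, matching 11.1.2 one for one.

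**Slip or deliberate exclusion?** Where 11.1.3 does leave out items of 11.1.2 (the overall and other-disease rows), the rows are simply absent. Here the rows are present, in the right positions, with the wrong prefix. That points to a labelling error. Each row is legible and has its own categories and reference level, so neither redaction nor a broken table explains it.

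**Is the gap filled elsewhere?**
- Section 6.3 has only the composite current-infection covariate, for serious infection, and no separate herpes zoster or tuberculosis item.
- In 11.1.3 the composite current-infection factor stays and is tested. The SAP does not say which diseases it contains.
- 11.1.2 and the tables by system organ class and preferred term in Section 8.2.2 still describe both conditions.

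**Extent on paper.** 2 factors × 11 reaction types = 22 factor-by-reaction cells, for each of the two time scopes in Section 8.2.3.2 (whole survey and first 6 months). This counts table cells and does not measure bias or lost precision.

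**Hemoglobin.** The union of the three classes covers all values except 9 to <10. Hemoglobin is not a factor in 6.3, 11.1.3 or 11.1.4, so only the one descriptive row is affected. The row is not marked as continuous data.

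**The case against.** The strongest reply is that this is a slip in two labels with little consequence. Much of that stands. The position of the rows makes the intention plain, and a programmer may already have used the complication variables, since the documents show the specification and not what was run. All tests are exploratory (SAP Section 4). The adjusted comparisons of malignant tumors and serious infections take their covariates from Section 6.3 and do not use 11.1.3. The documents give no number of patients with current herpes zoster or tuberculosis at baseline. If such patients are few, many of the cells would be close to empty.

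A reader might infer that current herpes zoster and tuberculosis are never examined as risk factors, or that 22 analyses per time scope have been lost. The documents do not support either. The composite current-infection factor is tested and may include these patients, past history of both conditions and tuberculosis prophylaxis are tested, and some analysis text is redacted and cannot be checked. The figure of 22 is only a row count.

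The reply does not remove the error. Section 5.4 makes 11.1.3 the operative list, so following it as printed omits two factors that its own structure shows were meant to be there.

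**Conclusion.** The point holds in a narrow form. As printed, 11.1.3 duplicates two past-history rows and lacks the two matching current-illness rows, so current herpes zoster and current tuberculosis are not listed as separate factors in the exploratory Xeljanz-group safety subgroup tests. The impact is minor: descriptive tabulation continues and the main between-group comparison is unaffected.

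This rests on reading the list literally and on the redacted text not supplying the two factors. How far the composite current-infection factor covers these patients cannot be settled from the documents.

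The hemoglobin gap is real but limited to one baseline row. A reader might infer that patients drop out of the baseline table. They are only unclassified in that row, and no risk-factor test uses it.

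**What to change.** In SAP 11.1.3, relabel the second herpes zoster row and the second tuberculosis-related row as complications. Then run the two factor analyses under Section 8.2.3.2 or, if the programs already used the complication variables, record that and correct the text. It would help to state which diseases the composite current-infection item contains.

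In SAP 11.1.2, make the hemoglobin classes contiguous, for example by adding ≥9 to <10. Other ways of closing the gap are possible, and the sponsor should confirm which classes were intended.

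The cost is a few corrected table rows and, at most, a rerun of the affected tables. The two complication variables are already defined in 11.1.2, so no new data are needed.
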